7.5.6 Change from baseline to each post-baseline assessment in PGA score

7.5.6.1 Variables

Group 1

The variable is derived as defined in Section 7.4.7.1 for each visit from Month 1 up to Month 12.

Group 2

The variable is derived as defined in Section 7.4.7.1 for each visit from Month 6 up to Month 12 based on the TP2 baseline value for all subjects in FAS-TP2.

7.5.6.2 Analysis

Group 1

The analysis will be based on an MMRM model, similar to the one used for the primary analysis [Section 7.2.5] based on 5 treatment groups as described in Section 5.4.3.3.

Group 2

The analysis will be based on an MMRM model, similar to the one used for the primary analysis [Section 7.2.5]. The model will be fitted including data from Month 7 up to Month 12 and from treatment groups *Cenerimod 2 mg / Ex-4 mg* and *Placebo / Ex-4 mg*. The model will include treatment group, month, TP2 baseline PGA score, treatment group by month interaction and TP2 baseline PGA score by month interaction as fixed effects.

All other aspects of the model are as described in Section 7.2.5.

7.5.7 Occurrence of flares and severe flares at each post-baseline assessment

7.5.7.1 Variables

Derived data for this endpoint is provided by an external vendor. Data will be categorized into mild/moderate or severe flares.

The definition of flares is provided in appendix 12 of the protocol [[D-22.031](#)].

7.5.7.2 Analysis

Group 1

Data will be analyzed descriptively as described in Section [7.4.4.2](#) for data up to Month 12 using treatment groups as described in Section [5.4.3.3](#).

Group 2

Data will be analyzed descriptively for all subjects in FAS-TP2 as described in Section [7.4.4.2](#) using treatment groups as defined in Section [5.4.3.2](#) for data from baseline TP2 up to Month 12.

7.5.8 Time to first severe flare from baseline to Month 12

7.5.8.1 Variables

Group 1

The variable is derived as defined in Section [7.4.5.1](#), for visits up to EOT (including TP2) and up to Month 12.

Group 2

The variable is derived as defined in Section [7.4.5.1](#), from the Month 6 visit up to EOT and up to Month 12 for all subjects in FAS-TP2. The censoring is derived from start of TP2, instead of start of TP1.

7.5.8.2 Analysis

Group 1

A Cox proportional hazards model will be performed as described in Section [7.4.5.2](#) based on 5 treatment groups as described in Section [5.4.3.3](#) for data up to EOT and up to Month 12.

Group 2

A Cox proportional hazards model will be performed with treatment as a factor, only including treatment groups *Cenerimod 2 mg / Ex-4 mg* and *Placebo / Ex-4 mg*.

7.5.9 Time to first flare from baseline to Month 12

7.5.9.1 Variables

Group 1

The variable is derived as defined in Section [7.4.6.1](#), for visits up to EOT + 180 days (including TP2) and up to Month 12.

Group 2

The variable is derived as defined in Section 7.4.6.1, from the Month 6 visit up to EOT + 180 days and up to Month 12 for all subjects in FAS-TP2. The censoring is derived from start of TP2, instead of start of TP1.

7.5.9.2 Analysis

Group 1

A Cox proportional hazards model will be performed as described in Section 7.4.6.2 based on 5 treatment groups as described in Section 5.4.3.3 for data up to EOT and up to Month 12.

Group 2

A Cox proportional hazards model will be performed with treatment as a factor, only including treatment groups *Cenerimod 2 mg / Ex-4 mg* and *Placebo / Ex-4 mg*.

7.5.10 Change from baseline to each post-baseline assessment up to Month 12 in prednisone or equivalent dose

7.5.10.1 Variables

Group 1

Steroids are collected on the Previous/Concomitant Medications eCRF page. OCS will be identified using the WHODrug Global B3/C3-format Standardized Drug Grouping named “Corticosteroids” and with CM.CMROUTE equal “ORAL”. Doses that are not taken daily will be transformed according to CM.CMDOSFRQ. OCS are converted to prednisone equivalent doses using the table in the protocol, appendix 1 [D-22.031]. If subjects are taking OCS during the study that are not covered in the table in the protocol, conversion factors are retrieved from the literature.

The prednisone or equivalent dose at each visit from baseline up to Month 12 will be derived as the monthly average of the daily prednisone or equivalent dose as shown in Table 9.

Table 9 Daily prednisone or equivalent doses used for derivation of monthly scores

Monthly score	First treatment day	Last treatment day
Baseline	-30	-1
Month 1	1	30
Month 2	31	60
Month 3	61	90
Month 4	91	120
Month 5	121	150
Month 6	Month 6 visit* – 29 days	Month 6 visit
Month 7	Month 6 visit + 1 day	Month 6 visit + 30 days
Month 8	Month 6 visit + 31 day	Month 6 visit + 60 days
Month 9	Month 6 visit + 61 day	Month 6 visit + 90 days
Month 10	Month 6 visit + 91 day	Month 6 visit + 120 days
Month 11	Month 6 visit + 121 day	Month 6 visit + 150 days
Month 12	Month 6 visit + 151 day	Month 6 visit + 180 days

* If a subject has a visit recorded after Month 6 but the Month 6 visit was not done, Month 6 visit will be replaced by Day 180.

It may be noted that for subjects with a Month 6 visit performed earlier than Day 180, there will be an overlap between the 29 days used to derive the Month 5 monthly score and the 29 days used to derive the Month 6 monthly score.

The absolute change in prednisone or equivalent dose from baseline (in TP1) is computed as follows:

$$\text{Change in prednisone or equivalent dose} = \text{Prednisone or equivalent dose at Visit X} - \text{prednisone or equivalent dose at baseline (in TP1)}.$$

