2.3 Study periods

2.3.1 Screening period

The screening period starts with the signing of the informed consent form and ends on the day of Randomization, before the first study drug intake. This period can last up to 60 days.

During this period, the subject's SLE background medication should be maintained stable except for OCS which should be tapered to the minimum required dose and maintained stable for at least 15 days prior to Randomization [see protocol section 5.2.2.1, [D-22.031](#)].

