5.2 Baseline

- The **‘Baseline (TP1)’** value for **efficacy and safety analyses** is defined as the last non-missing value recorded prior to first study drug intake in TP1 for each endpoint and each subject individually. For subjects that were randomized but did not take any study drug, baseline (TP1) is defined as the last non-missing value recorded up to and including the day of Randomization.
- The **‘Baseline (TP2)’** value for **efficacy and safety analyses** is defined as the last non-missing value recorded up to and including the day of re-randomization for each endpoint and each subject individually. This baseline is only defined for subjects that have been re-randomized by IXRS.

For certain datasets/analyses an **‘intra-day baseline’** is derived (e.g., ECG, vital signs). This intra-day baseline is defined as the last non-missing assessment prior to study drug intake on the corresponding day. If there is no pre-dose assessment on the day (by time and date), then the intra-day baseline is considered to be missing. The intra-day baseline is calculated for parameters that are part of the hourly measurements on the day of first study drug intake (in TP1) and the day of first study drug intake of a re-initiated subject (in TP1).

For datasets where multiple measurements exist for the selection of the baseline assessment, the definition(s) is/are provided in the corresponding sections (e.g., spirometry or ECG data).

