FACIT-Fatigue, PGIS-F, PGIC-F, SF-36v2™, and Lupus QoL		X		
Chest X-ray ⁽⁵⁾		X		
Vital signs: SBP/DBP* ^{(6) (7)}		X	X	
12-lead ECG* ⁽⁷⁾		X	X	
ECG Holter* ⁽⁸⁾			X	X
Echocardiography ⁽⁴⁾		X		
Spirometry*		X		
Ophthalmological examinations		X		
OCT		X		
PK sampling* ⁽⁹⁾			X	

PERIODS	Name	UNSCHEDULED		
	Duration	NA		
VISITS	Number	U1, U2, ...	I1	I2
	Name	Unscheduled ⁽¹⁵⁾	Re-initiation	
	Time	Any day between Day 1 and EOS (assessments to be performed as applicable)	Re-initiating study drug after interruption lasting more than 7 days between Day 1 and Day 14	
Hematology and blood chemistry* ⁽¹⁰⁾		X		
Pregnancy test ⁽¹¹⁾		X		
Viral serology / TB test		X		
Urinalysis (dipstick)		X		
SLE biomarkers		X		
Urine protein-to-creatinine ratio		X		
Study treatment dispensing/return and accountability			X	
AEs ⁽¹²⁾ / SAEs ⁽¹²⁾		X	X	

One month is considered to be 30 days.

Day 1 (date of Randomization visit) is to be used as the reference date for the purpose of calculating the subsequent visit dates (and time windows).

For WOCBP, the serum pregnancy test at Visit 1 must be performed at least 3 weeks before the urine pregnancy test performed at Visit 2 prior to Randomization.

* Study treatment should not be taken before the assessment (i.e., SBP/DBP, ECGs, spirometry, laboratory tests, and PK sampling).

- (1) Prior to Randomization, the following central laboratory results must be available to confirm eligibility: ANA, anti-dsDNA, anti-HAV IgM, Hepatitis B surface antigen, Hepatitis C antibodies (anti-HCV IgG or IgM), anti-HEV IgM and/or IgG, HEV-RNA PCR (as needed), HIV1 and HIV2, varicella-zoster virus IgM antibody, urine protein-to-creatinine ratio, ALT/AST/TBIL and pregnancy test (if applicable).
- (2) A complete physical examination (i.e., inspection, percussion, palpation, and auscultation) will only be performed at Visits 1, 2, 3, 5, 8, 11, 14, and 15. For all other visits, a symptom-driven abbreviated physical examination will be performed in order to capture assessments needed for the SLEDAI-2K, the PGA, the BILAG, and the SFI.
- (3) Height only at Screening. Body weight should be measured as part of BILAG assessment at each applicable visit and recorded in the source documentation. If clinically relevant, body weight collected outside Screening, EOT and EOS visits may be reported as an Unscheduled assessment.

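### The 30-day baseline window for prednisone-equivalent dose can reach back into the screening steroid taper, so part of a pre-treatment reduction can be reported as on-study change

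*SAP*

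**What the plan says.** SAP 7.5.10.1 converts OCS to prednisone equivalents. The value at each visit from baseline to Month 12 is "derived as the monthly average of the daily prednisone or equivalent dose". Table 9 gives the windows: baseline is Days -30 to -1, Month 1 is Days 1 to 30, and later months follow in 30-day blocks. "The absolute change in prednisone or equivalent dose from baseline (in TP1) is computed as follows": the dose at the visit minus the dose at baseline.

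SAP 2.3.1 describes screening: "This period can last up to 60 days". Background SLE medication is to stay stable in that time, apart from "OCS which should be tapered to the minimum required dose and maintained stable for at least 15 days prior to Randomization".

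SAP 5.2 defines the TP1 baseline for efficacy and safety as the "last non-missing value recorded prior to first study drug intake in TP1". It also lets individual sections set their own baseline where several measurements exist. SAP 7.5 defines the baseline for all randomized subjects (Group 1), to which this endpoint belongs, as the last measurement available before randomized treatment starts.

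Under SAP 7.5.10.2 the change during TP1 is summarized descriptively by visit and treatment group, with a figure. No model or test is planned.

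**The concern.** The baseline window is 30 days long, but stability is required for only 15 of them. Table 9 has no rule that removes taper doses from the other 15. A subject who steps down between Day -30 and Day -16 gets a baseline above the dose actually taken when treatment starts. Every later visit is compared with that raised value, so a reduction made before the first dose appears as on-study change, beginning at Month 1.

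The situation need not be rare. For women of childbearing potential, SAP 12.1 says "the serum pregnancy test at Visit 1 must be performed at least 3 weeks before the urine pregnancy test performed at Visit 2", so screening may be as short as about three weeks. If screening lasts 30 days or less, any taper made during it falls within the baseline window.

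At stake is the reading of the by-arm table and figure, where the within-arm change is what is displayed. Baseline can also disagree with the stratification variable, which is the OCS dose at Randomization. For example, an assumed step from 10 to 5 mg/day on Day -15 puts the subject in the stratum below 7.5 mg/day, with a Table 9 baseline of (15 × 10 + 15 × 5)/30 = 7.5 mg/day.

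**Working it through.** The plan states no figure for this endpoint that could be reproduced. The check is day-count arithmetic.

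**Inputs from the SAP.** Baseline window Days -30 to -1, 30 days (Table 9). Stable period at least Days -15 to -1, 15 days (2.3.1). About 325 subjects in five equal arms, so about 65 per arm (2.1).

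**Inputs assumed.** The documents give neither the share of subjects who taper nor the taper size. The ranges used are 0 to 50% of subjects and steps of 2.5 to 5 mg/day.

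**One subject, single step.** The dose goes from D0 to D1, the first day at D1 is Day -t with t ≥ 15, and nothing changes on treatment. Then

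apparent change = -(D0 - D1) × max(0, 30 - t)/30.

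| New dose starts | Share of step counted | Baseline, 10 to 7.5 mg/day (assumed) | Apparent change (mg/day) |
|---|---|---|---|
| Day -15 | 15/30 = 50% | (15 × 10 + 15 × 7.5)/30 = 8.75 | -1.25 |
| Day -20 | 10/30 = 33% | (10 × 10 + 20 × 7.5)/30 = 8.33 | -0.83 |
| Day -25 | 5/30 = 17% | (5 × 10 + 25 × 7.5)/30 = 7.92 | -0.42 |
| Day -30 or earlier | 0% | 7.50 | 0 |

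A linear taper spread over Days -30 to -16 counts 25% of the step. If the same taper starts on Day -45, the share is 13%; from Day -60 it is 9%.

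**Arm mean, upper limit.** With share p tapering by step S, all reaching the new dose on Day -15, the artefact is -p × S × 0.5:

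- p = 0: 0
- p = 10%: -0.125 (S = 2.5) to -0.25 (S = 5) mg/day
- p = 30%: -0.375 to -0.75 mg/day
- p = 50%: -0.625 to -1.25 mg/day

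**Arm mean, spread-out timing.** Let the first day at the new dose be uniform over the 46 days from Day -60 to Day -15. The average share counted is (1 + 2 + … + 15)/30/46 = 4/46 = 8.7%. With steps of 2.5 and 5 mg/day equally likely (mean 3.75), the artefact is about -p × 3.75 × 0.087, or -0.03, -0.10 and -0.16 mg/day for p = 10%, 30% and 50%. A simulation of five arms of 65 (4,000 runs per setting) gave the same values. All five arms were below zero in 55%, 99.5% and 100% of runs. The mean difference between an active arm and placebo was about 0 (at most 0.0012 mg/day in size), with a standard deviation of 0.04, 0.06 and 0.08 mg/day.

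**After the change.** With baseline taken over Days -15 to -1, or as the last dose before first intake, the 10 to 7.5 example has baseline 7.5 and change 0. The same holds for any subject who met the 15-day rule.

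**The case against.** The strongest defence is that SAP 5.2 expressly allows endpoint-specific baselines and Table 9 is one. It compares a 30-day mean with 30-day means, which is a coherent choice, and a shorter baseline gives up that symmetry. This stands as far as it goes: departing from the general definition is not in itself an error. But nothing in 7.5.10 deals with the taper, and equal window lengths do not help when half of the baseline window may lie before the stable period.

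A second defence is that many subjects contribute nothing: those not on OCS, those already at their minimum dose, and those at the new dose by Day -30. SAP 2.3.1 refers to protocol section 5.2.2.1 for the OCS rules. That section is not in the protocol document available here, which is the COVID-19 addendum, so any limits it sets on taper timing or size cannot be checked. This stands, and it is why no arm-level size can be claimed.

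A third is that randomization follows the taper and is stratified by OCS dose at Randomization. The artefact is then the same across arms in expectation, and placebo is shown beside every dose. This also stands. A reader might infer that the window distorts the comparison with placebo, or creates an apparent drug effect, but the design does not support that. Uneven taper timing adds some scatter between arms, which was small under the assumptions tried, and no formal comparison is planned.

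**Conclusion.** The point holds in a limited form. The baseline window is twice the required stable period, so for a subject who tapers in Days -30 to -16 and then meets the 15-day rule, up to half of the taper step is reported as on-study reduction. Under the taper that the SAP describes, the bias runs in one direction, toward steroid reduction within each arm.

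A reader might go further and conclude that baseline always contains the taper and that every arm will show a spurious fall. The documents do not establish that. They say nothing on how many subjects taper, by how much or when. The mg/day figures above rest on assumed doses and shares, and the timing-dependent range starts at zero. Depending on those assumptions, the arm-mean artefact runs from 0 to -1.25 mg/day. It was -0.03 to -0.16 mg/day when timing was spread across screening and 10 to 50% of subjects tapered.

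No error rate and no primary or secondary result is affected. It is still worth correcting, because the bias is avoidable and the by-arm display is the endpoint's only planned output.

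**What to change.** In Table 9, replace the baseline row with one of two definitions:

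- the mean daily prednisone-equivalent dose over Days -15 to -1; or
- the last daily dose before first study drug intake, which agrees with SAP 5.2 and 7.5.

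Leave all post-baseline windows unchanged. The 30-day mean can be kept as a sensitivity summary, which would also show how much the taper matters in practice.

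The cost is one table row and the matching line of derivation code. The daily doses are already collected, and no clinical rule changes. The downside is that baseline is averaged over fewer days than the post-baseline months, or over a single day with the second option. With the first option, a subject who did not meet the 15-day stability rule could still carry some taper into baseline.

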## 2.4 Efficacy assessments

### 2.4.1 Study assessments related to the primary and secondary endpoints.

It is important to ensure that efficacy assessments, especially assessments related to primary (SLEDAI-2K) and secondary endpoints (i.e., BILAG and SRI-4) are performed as per protocol. They should ideally not be performed later than one month after the protocol planned schedule of assessment [see protocol section 7].

If the investigator is not able to arrange on-site visits to perform the planned efficacy evaluations, the following should be implemented:

- Organize the remote visit as described above, at approximately the time of the planned visit assessment.
- During the remote visit, the investigator should collect the SLEDAI-2K components even if not all assessments are possible [protocol section 7.2.6]. Record the outcome of the SLEDAI-2K assessment in the eCRF and report a PD related to COVID-19 in the event of missing values. If this is not possible, the investigator should contact the CRA or sponsor study team.
- The same procedures should be followed to perform the assessments (e.g., BILAG, PGA, SLE Flare Index) related to the secondary efficacy endpoints. These measurements should be collected at that time as well [protocol section 7.2.6].

**Very important note:** as soon as the study site can resume activity, ask the subject to come to the site at the closest scheduled visit, to perform a full SLEDAI-2K assessment and all other assessments (such as BILAG, PGA, ...) which will be recorded in the eCRF.

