2 STUDY DESIGN AND FLOW

2.1 Study design

This is a Phase 2b, multicenter, randomized, double-blind, placebo-controlled, parallel group study to evaluate the efficacy, safety, and tolerability of cenerimod in subjects with moderate to severe SLE.

Approximately 325 adult subjects with SLE will be randomized in a 1:1:1:1:1 ratio to placebo, 0.5, 1, 2, or 4 mg once daily of cenerimod, in addition to background SLE therapy.

Once randomized, all subjects will enter a 6-month double-blind study treatment period defined as Treatment Period 1 (TP1).

Subjects randomized to, and still receiving, placebo, 0.5, 1, or 2 mg at Month 6 will continue their study treatment up to an additional maximum of 6 months in Treatment Period 2 (TP2), for a total maximum of 12 months.

Subjects randomized to the 4 mg arm will receive study treatment at this dose for a maximum of 6 months in TP1. Afterwards, subjects in this group, still receiving this dose

at Month 6, will be re-randomized in a 1:1 ratio to placebo or cenerimod 2 mg to enter TP2 and will continue for a total maximum of 12 months

Subjects who discontinue treatment in TP1 will continue study FU, performing study assessments, up to maximum duration of 12 months.

At EOT, subjects will enter a 6-month FU period (4-month before protocol Version 5).

Treatment allocation is stratified by dose of OCS at Randomization (two strata: < 7.5 mg/day or ≥ 7.5 mg/day prednisone or equivalent), and by disease activity at Screening (with two strata: mSLEDAI-2K < 10 or ≥ 10).

The study will be conducted at approximately 180 sites in 21 countries notably from the regions of Asia Pacific, Eastern Europe, Latin America, North America, and Western Europe.

No interim analysis is planned. There will be three study analyses: the Month-6 analysis, the Month-12 analysis and the final EOS analysis. Month-6 analysis will be performed when all randomized subjects have completed TP1 or discontinued the study. Month-12 analysis will be performed when all randomized subjects have completed TP2 or discontinued the study. Final EOS analysis will be performed when all randomized subjects have completed the post-treatment follow-up period or discontinued the study.

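### Table 9 of the SAP changes its anchor at Month 6, so a Month 6 visit after Day 180 leaves some steroid days in no monthly score

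*SAP*

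**What the plan says.** SAP 7.5.10.1 derives the dose at each visit as the average daily dose over the window in Table 9. Month 5 is fixed in days from the start of treatment ("Month 5 121 150"). Month 6 starts at "Month 6 visit* – 29 days" and ends at the visit. Months 7 to 12 follow in 30-day blocks from the Month 6 visit, the last ending at "Month 6 visit + 180 days".

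Two special cases are covered. If the Month 6 visit was not done but a later visit exists, "Month 6 visit will be replaced by Day 180". The SAP also remarks that "for subjects with a Month 6 visit performed earlier than Day 180, there will be an overlap" between Months 5 and 6. Nothing is said about a Month 6 visit after Day 180.

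Visits themselves keep one anchor. Under SAP 12.1, "Day 1 (date of Randomization visit) is to be used as the reference date for the purpose of calculating the subsequent visit dates". SAP 2.1 states that subjects on placebo, 0.5, 1 or 2 mg "will continue their study treatment up to an additional maximum of 6 months in Treatment Period 2 (TP2), for a total maximum of 12 months", and re-randomized 4 mg subjects have the same 12-month limit. At 30 days per month, planned Month 12 is Day 360. SAP 7.5.10.2, in the text available, summarizes and plots the change by visit and treatment group over TP1.

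**The concern.** Two anchors meet between Month 5 and Month 6, and they join exactly only when V = 180. An early visit makes the windows overlap, which the SAP acknowledges. A late visit pulls them apart, and oral steroid taken on the days between is dropped from every monthly score. No protocol deviation is needed: any visit on Days 181 to 187 is in window and has this effect.

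What a subject's record shows around Months 5 and 6 then depends partly on visit timing rather than on steroid use. A short course could be missing from the TP1 table and figure although it was recorded as concomitant medication. The same shift carries through to Month 12, whose window moves with the Month 6 visit while the planned visits do not.

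**Working it through.** **Inputs.** Table 9 gives Month 5 = Days 121 to 150, Month 6 = V-29 to V, Month 11 = V+121 to V+150 and Month 12 = V+151 to V+180. The schedule in SAP 12.1 allows Month 6 on Day 180 ±7, so V = 173 to 187. SAP Table 4 takes Month 6 as Days 166 to 195 and Month 12 as Days 346 to 375, with target Day 360. I assume that the first dose is taken on the randomization day, so that Table 9 and the schedule share Day 1.

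**The SAP's own statement first.** Overlap of Months 5 and 6 = 150 - (V-29) + 1 = 180 - V when V < 180. V = 179 gives 1 day and V = 173 gives 7, so the remark reproduces. Its description of each window as 29 days does not: 150 - 121 + 1 = 30, and V - (V-29) + 1 = 30.

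**Late visit.** Days in no window = (V-29) - 151 = V - 180 when V > 180. The Month 12 window ends at V + 180, which is V - 180 days after Day 360.

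| V | Month 6 window | Overlap with Month 5 | Days in no window before Month 6 | Month 12 window | Days past Day 360 |
|---|---|---|---|---|---|
| 166 | 137–166 | 14 | 0 | 317–346 | 0 (ends 14 short) |
| 173 | 144–173 | 7 | 0 | 324–353 | 0 (ends 7 short) |
| 180 | 151–180 | 0 | 0 | 331–360 | 0 |
| 181 | 152–181 | 0 | 1 (Day 151) | 332–361 | 1 |
| 187 | 158–187 | 0 | 7 (151–157) | 338–367 | 7 |
| 195 | 166–195 | 0 | 15 (151–165) | 346–375 | 15 |

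The lost days end at V-30. They lie between the two windows and not immediately before the Month 6 visit.

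**Month 12 against actual end of treatment.** SAP 2.3.2 ends TP2 at the Month 12 visit (Day M). For a subject treated until then, days after treatment in the window = max(0, V + 180 - M).

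- V = 187: M = 353 gives 14, M = 360 gives 7, M = 367 gives 0.
- V = 195: M = 360 gives 15, M = 375 gives 0.

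Concomitant therapy is still recorded at FU1 and EOS (SAP 12.1), so doses on such days would exist in the data.

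**Size for one subject (assumed doses).** Take a course filling the 7 lost days at V = 187, with an excess of 10, 20 or 40 mg/day over the usual dose. Averaged over Days 151 to 187 (37 days), it would add 70/37 = 1.9, 140/37 = 3.8 or 280/37 = 7.6 mg/day. Under Table 9 it adds nothing to any month. With about 325/5 = 65 subjects per arm, one such subject moves an arm mean by 1.9/65 = 0.03 to 7.6/65 = 0.12 mg/day.

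**The case against.** The best defence is that Table 9 derives a dose at each visit. Separate visit averages need not tile the calendar, and anchoring Month 6 on the visit keeps a 30-day window and keeps TP2 days out of it. The trial is blinded, nothing in the documents suggests that visit timing differs by arm, and one subject hardly moves an arm mean. All of this stands as to size. It does not explain why the SAP discloses the overlap and not the gap, or leaves a late visit without a rule when a missed visit has one.

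Two stronger readings are tempting, and the documents support neither.

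- *The Month 12 score runs into follow-up whenever Month 6 is late.* This equates the end of treatment with Day 360. TP2 ends at the actual Month 12 visit, and an equally late Month 12 visit gives no overrun. The analysis text available for this variable covers TP1 only, so no described output tabulates Months 7 to 12. Further text may be absent from the copy reviewed.
- *A Month 6 visit one month late, on Day 210, would lose a full 30 days and put the whole Month 12 window after Day 360.* The COVID-19 addendum (2.4.1) says of efficacy assessments: "They should ideally not be performed later than one month after the protocol planned schedule of assessment". But Table 4 assigns Day 210 to Month 7 (Days 196 to 225), SAP 7.5 applies those windows to the exploratory endpoints, and addendum 2.2 skips a delayed visit that falls within about a week of the next one. Month 6 then counts as not done, the Day 180 substitute applies, and both the gap and the excess are zero.

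**Conclusion.** The gap is real and follows from Table 9 alone. A Month 6 visit after Day 180 leaves V-180 days in no monthly score: up to 7 within the visit schedule and up to 15 within Table 4. It affects the planned TP1 by-visit summary of an exploratory, descriptive endpoint. No primary or secondary inference is touched. The effect on arm means is likely small, though a single subject's profile can change noticeably under the doses assumed above.

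The Month 12 part is conditional. The window passes planned Day 360 by V-180 days, but it includes days after the subject's actual end of treatment only if the Month 12 visit is less late than Month 6 was, for example 7 of 30 days with V = 187 and a Month 12 visit on Day 360. It concerns derived scores rather than an analysis described in the available text.

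The 15-day limit assumes that the Month 6 visit in Table 9 is the one selected by Table 4, which Table 9 does not say.

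**What to change.** In Table 9 and its notes:

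1. When V is after Day 180, define Month 6 as Day 151 to the Month 6 visit, averaged over the actual number of days. Leave the rule for earlier visits and its overlap note as they are.
2. Define Month 12 as the 30 days ending at the actual Month 12 visit, or at Day 360 if that visit was not done, mirroring the Month 6 rule. No day after that visit then enters the score.
3. State that the Month 6 visit means the visit selected by Table 4.
4. Change 29 days to 30 in the overlap note.

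The cost is a table edit and a small programming change. There are two downsides. Month 6 windows vary in length, to 187 - 150 = 37 days at V = 187 and 195 - 150 = 45 at V = 195, which is why the divisor must be the actual number of days.

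Months 11 and 12 will also no longer always join. They overlap by 180 - (M-V) days when M-V is below 180, and leave (M-V) - 180 days between them when it is above. V = 187 with M = 360 gives a 7-day overlap; V = 173 with M = 360 gives a 7-day gap. At the extremes of Table 4 (V = 195 with M = 346, or V = 166 with M = 375) either can reach 29 days. These equal the days by which the present Month 12 window runs past, or stops short of, the Month 12 visit, so the mismatch is moved to before the visit and not enlarged. It should be noted in the SAP as for Months 5 and 6.
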